6.1.4. General Medical History

For participants in the FAS, general medical history will be summarized. This summation will include the number and percentage of participants with significant medical history for each body system/organ class as documented on the CRF.

6.2. Disposition of Participants

The number and percentage of participants who were treated, completed the study, discontinued study treatment with a primary reason for discontinuation, and discontinued from the study with a primary reason for withdrawal will be summarized for the FAS. The number of participants enrolled by site will also be provided.

6.3. Protocol Deviations and Violations

Protocol deviations and violations recorded on the CRF will be presented in the participant data listings and tables.

6.4. Exposure

For participants in the FAS, descriptive statistics will be provided for duration of treatment, average daily dose, and total dose. Duration of treatment with INCB054707 is defined as the number of days from Day 1 to the date of last record of INCB054707 administration.

6.5. Study Drug Compliance

For participants in the FAS, overall compliance (%) for INCB054707 will be calculated for all participants as

Compliance (%) = $100 \times [\text{total number of tablets dispensed} - \text{total number of tablets returned}] / [\text{total intended number of tablets}].$

• The total intended number of tablets will be based on the earliest study day of permanent discontinuation of the study drug or last study drug record in the database.

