4.2. Overall Study Duration

The study will consist of a screening period of up to 28 days, an 8-week open-label, single-arm treatment period, and a 4-week safety follow-up period. The estimated total duration of study participation is approximately 16 weeks for each participant.

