6. STUDY TREATMENT

6.1. Study Treatment Administered

Information regarding study drug and administration is provided in Table 6. Participants will record study drug administration in a daily diary. Participants will take the study drug once daily, preferably in the morning.

Table 6: Study Treatment Information

Study treatment name:	INCB054707
Dosage formulation:	Tablet
Unit dose strength/dosage level:	INCB054707 15 mg QD
Route of administration:	Oral
Administration instructions:	INCB054707 will be taken orally with water without regard to food.
Packaging and labeling:	INCB054707 will be provided as 15 mg tablets and labeled as required per country requirement.
Storage:	Ambient (15°C-30°C/59°F-86°F)

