6.5. Dose Modifications

In some circumstances, it may be necessary to temporarily interrupt treatment with INCB054707 as a result of AEs or laboratory abnormalities that have an unclear relationship to the study drug (see Table 7). Except in cases of emergency, it is recommended that any laboratory findings be confirmed and that the investigator consult with the sponsor medical monitor (or other representative of the sponsor) before temporarily interrupting study drug.

Table 7: Guidelines for Interrupting, Restarting, and Discontinuing Study Drug

ADVERSE EVENT	ACTION TAKEN	
Chemistry		
AST and/or ALT > 3.0 × ULN	 Step 1: Interrupt study drug administration up to 2 weeks (14 days) until the toxicity has resolved to ≤ 3.0 × ULN. Step 2: Restart study drug, and monitor as clinically indicated. 	
AST and/or ALT > 5.0 × ULN	Discontinue study drug administration, and monitor as described in Section 9.3.	
Hematology		
Platelet counts 50 to ≤ 100 × 109/L or ≥ 50% decrease from baseline	Step 1: Interrupt study drug administration up to 2 weeks (14 days) until the toxicity has resolved to $> 100 \times 10^9/L$.	
	Step 2: Restart study drug, and monitor as described in Section 9.3.	
$ANC \le 1.0 \times 109/L$	Step 1: Interrupt study drug administration up to 2 weeks (14 days) until the toxicity has resolved to $> 1 \times 10^9/L$ or the baseline value.	
	Step 2: Restart study drug, and monitor as clinically indicated.	
Hemoglobin 8 to ≤ 10 g/dL	Step 1: Interrupt study drug administration up to 2 weeks (14 days) until the toxicity has resolved to > 10 g/dL.	
	Step 2: Restart study drug, and monitor as clinically indicated.	
 Platelet count < 50 × 10⁹/L ANC < 0.5 × 10⁹/L 	Discontinue study drug administration, and monitor as described in Section 9.3.	
• ANC ≤ 1.0 × 10 ⁹ /L with an oral temperature of at least 38.5°C OR with ≥ Grade 3 infection		
• Hemoglobin < 8 g/dL		

Table 7: Guidelines for Interrupting, Restarting, and Discontinuing Study Drug (Continued)

ADVERSE EVENT	ACTION TAKEN	
Other toxicities		
Any Grade 1 or Grade 2 toxicity	Continue study drug and treat the toxicity; monitor as clinically indicated.	
Any Grade 3 toxicity except those that are clearly and incontrovertibly due to underlying disease or extraneous causes	 Step 1: Interrupt study drug up to 2 weeks (14 days), until toxicity resolves to ≤ Grade 1. Step 2: Restart study drug and monitor as clinically indicated. 	

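### Read literally, the SAP compliance formula counts days of temporary drug interruption as intended dosing days, so a single 14-day hold can lower a fully adherent participant's figure to 75%

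*SAP*

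**What the plan says.** SAP 6.5 states that "overall compliance (%) for INCB054707 will be calculated for all participants as" 100 times tablets dispensed minus tablets returned, divided by total intended tablets. The only rule for the denominator is that the "total intended number of tablets will be based on the earliest study day of permanent discontinuation of the study drug" or on the last study drug record in the database.

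Protocol 6.1 supplies the drug as 15 mg tablets for a 15 mg daily dose and says "Participants will take the study drug once daily, preferably in the morning". Protocol 4.2 sets "an 8-week open-label, single-arm treatment period, and a 4-week safety follow-up period".

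Protocol 6.5 allows temporary interruption for adverse events or laboratory abnormalities. For raised AST or ALT, low platelets, low ANC, low hemoglobin and most Grade 3 toxicities, the first step in Table 7 begins "Interrupt study drug administration up to 2 weeks (14 days", and the second step is to restart.

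For exposure, SAP 6.4 says that "descriptive statistics will be provided for duration of treatment, average daily dose, and total dose". It defines duration as running from Day 1 to the last recorded administration, again without a deduction for held days. Protocol 6.4 (Study Treatment Compliance) relies on tablet counts and does not mention interruptions.

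**The concern.** A participant whose drug is held and then restarted goes on towards Week 8, so the last drug record falls after the hold. The held days then lie inside the period used to count intended tablets. The unused tablets come back and reduce the numerator, while the denominator stays the same.

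The percentage therefore combines two different things: doses the participant failed to take, and doses the investigator withheld. Safety and tolerability is the primary objective, so the participants with holds are the ones whose records will be read most closely. They are also the ones whose compliance would be understated. With about 10 participants, one such case shows in both the mean and the minimum.

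**Working it through.** The documents state no compliance figure, so there is none to reproduce. The check applies the SAP 6.5 formula directly.

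**Inputs**
- One tablet per day: 15 mg tablets, 15 mg once daily (Protocol 6.1, Table 6).
- Treatment period: 8 weeks = 56 days (Protocol 4.2). The Week 8 window of ±3 days (Protocol Table 3) gives 53 to 59 days.
- Hold length: up to 14 days (Protocol Table 7).
- Sample: about 10 participants (Protocol Table 2).
- Assumed: every tablet outside the hold is taken, all unused tablets are returned, and dosing restarts after the hold.

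**Formulas.** Let T be the days from Day 1 to the last drug record and h the held days.
- SAP 6.5 read literally: 100 × (T − h) / T.
- Held days removed from the denominator: 100 × (T − h) / (T − h) = 100%.

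**Results, fully adherent participant**

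| T | h | Tablets used | Literal SAP 6.5 | Held days removed |
|---|---|---|---|---|
| 56 | 7 | 49 | 49/56 = 87.5% | 49/49 = 100% |
| 56 | 14 | 42 | 42/56 = 75.0% | 42/42 = 100% |
| 53 | 14 | 39 | 39/53 = 73.6% | 39/39 = 100% |
| 59 | 14 | 45 | 45/59 = 76.3% | 45/45 = 100% |

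**Can the measure tell a hold from missed doses?** A participant with no hold who misses 14 tablets also has 42/56 = 75.0%. A participant with a 14-day hold who misses 3 further tablets has 39/56 = 69.6% under the literal rule. With held days removed the figure is 39/42 = 92.9%, which reflects the three missed tablets alone.

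**Effect on the mean.** One participant at 75% and nine at 100%: (9 × 100 + 75)/10 = 97.5%, a fall of 2.5 points. The one-in-10 frequency is an assumption.

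**Overlap with exposure.** The SAP gives no formula for average daily dose. If it is total dose over duration, the 14-day case gives 42 × 15/56 = 11.25 mg, which is 75% of 15 mg. Under the literal rule, compliance then repeats what average daily dose already shows.

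**A hold that ends in permanent discontinuation.** Suppose the last dose is on Day 28 and a 14-day hold follows. If the count stops at the last dose, compliance is 28/28 = 100%. If it runs to the end of the hold, compliance is 28/42 = 66.7%. Subtracting held days gives 28/28 = 100% in both cases.

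**The case against.** The strongest reply is that SAP 6.5 does not expressly count held days. It sets an end date for the count, and a programmer could take the word intended to exclude days on which drug was withheld. That stands: 75% is what the literal reading produces, not a figure the SAP commits to. But the end date is the only rule written, so exclusion would rest on the programmer's judgement.

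A reader might infer three stronger points, none of which the documents support.

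- **That the protocol strictly mandates these holds.** Table 7 is titled as guidelines. Its lead-in says interruption may be necessary, and recommends confirming laboratory findings and consulting the medical monitor beforehand except in emergencies.
- **That 75% is typical.** Table 7 sets 14 days as an upper limit, so 75% is the largest effect of a single hold in a 56-day course. The documents give no expected frequency of holds.
- **That tolerability or efficacy conclusions would be distorted.** The full analysis set is used for all efficacy and safety data (SAP 5.3.1). There is no compliance threshold and no per-protocol set. Under Protocol 7.1.1, noncompliance that might lead to discontinuation is a matter of investigator opinion and sponsor consultation, not of this percentage.

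Holds are also visible elsewhere. SAP 8.2.2 and planned Table 3.2.14 report adverse events leading to interruption, Listing 3.2.5 covers the same events, and SAP 6.4 gives average daily dose. With about 10 participants, a reader could match a low value to its hold. This makes misreading less likely, but it leaves the summary percentage uncorrected.

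**Conclusion.** The point holds as a defect in one descriptive measure. As written, SAP 6.5 has no deduction for temporary interruptions, and the literal calculation gives an adherent participant 75% for a full 14-day hold and 87.5% for a 7-day hold. These are the values given to someone who skips that many doses. The figures assume restart after the hold, 56 days to the last drug record and complete intake otherwise; the Week 8 window moves the 14-day figure between 73.6% and 76.3%. The 97.5% mean rests on the further assumption of one such case in 10 with all others at 100%.

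The reach is limited to planned Table 3.1.1 and the Study Drug Compliance listing. The change is worth making because it is easy, not because a conclusion of the trial depends on it.

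**What to change.** In SAP 6.5, define total intended tablets as the number of days from Day 1 to the earlier of the last drug record or permanent discontinuation, minus days of investigator-directed interruption, at one tablet per day. Leave average daily dose in SAP 6.4 to show the effect of holds on exposure.

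The cost is one sentence and a small programming change. It depends on one check: the sponsor must confirm that interruption start and stop dates are in the study drug administration data. The documents suggest this but do not show it. Protocol 9.3 records the action taken with study drug for each adverse event, Protocol 6.1 has participants record dosing in a daily diary, and the SAP plans a Study Drug Administration listing whose fields are not given. The change affects only the calculation and leaves every interruption rule in Table 7 as it is.

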6.6. Prior and Concomitant Medication

For participants in the FAS, prior medications and concomitant medications will be coded using the WHO Drug Dictionary and summarized by WHO drug class and WHO drug term. Results will be summarized as number and percentage of participants with prior and concomitant medications by PT and WHO drug class.

7. EFFICACY

All efficacy analyses are exploratory. Hence, no p-values will be provided, and multiple adjustment will not be made.

7.1. Efficacy Parameters

An example of the lesion count worksheet is provided in Appendix B and will be used for assessment of Hurley Stage, HiSCR, modified Sartorius scale,

It includes assessment of 12 anatomic regions:

- Left/right axilla,
- Left/right sub/inframammary area,
- Intermammary area,
- Left/right buttock,
- Left/right inguino-crural fold,
- Perianal area, perineal area, and
- Other areas.

Additionally, the need for rescue lesional treatment, including number of interventions, will be documented in this worksheet.

7.1.1. Hurley Stages of Hidradenitis Suppurativa

Hurley Stages of HS are defined in Table 2. The investigator will determine the Hurley Stage in each affected anatomical region at the designated study visits. If more than 1 stage is present in a region, the worst stage in each region should be documented. The participant is assigned Hurley Stage corresponding to the Hurley Stage of his or her worst involved anatomic region.

Table 2: Hurley Stages of Hidradenitis Suppurativa

Stage	Description
I	Abscess formation (single or multiple) without sinus tracts and cicatrization
II	Recurrent abscesses with tract formation and cicatrization; single or multiple, widely separated lesions
III	Diffuse or near-diffuse involvement or multiple interconnected tracts and abscesses across the entire area

7.1.2. Hidradenitis Suppurativa Clinical Response (Abscess and Inflammatory Nodule Count)

A HiSCR definition is based on the following criteria relative to baseline at each visit:

- At least 50% reduction in total of counts of the AN, and
- No increase in abscess count, and
- No increase in draining fistula count (see Appendix B; Kimball et al 2016).

7.1.3. Modified Sartorius Scale

The modified Sartorius scale is a measure of the severity of HS (see Appendix B; Sartorius et al 2003). The total Sartorius score is the sum of 12 anatomic region Sartorius scores. A larger score denotes a more severe disease status. The regional Sartorius score can be calculated as follows, using the parameters in Table 3:

Regional Sartorius Score = Region + $(2 \times \text{Number of Inflammatory Nodules})$ + $(2 \times \text{Number of Non-Inflammatory Nodules})$ + $(4 \times \text{Number of Abscesses})$ + $(4 \times \text{Number of Draining Fistules})$ + $(4 \times \text{Number of Non-Draining Fistules})$ + $(1 \times \text{Number of Hypertrophic Scars})$ + Distance + Separate.

Table 3: Sartorius Score

Region	0	Otherwise	
	3	If any lesion count in this anatomic region > 0	
Distance	0	If no active lesion	
	2	If longest distance between two relevant lesions or size < 50mm	
	4	If longest distance between two relevant lesions or size ≥ 50 mm and < 100 mm	
	6	If longest distance between two relevant lesions or size ≥ 100 mm	
Separate	0	If all lesions clearly separated by normal appearing skin	
	6	Otherwise	

7.1.4. Need for Rescue Lesional Treatment

Study procedures must be performed before any interventions. Any lesion undergoing an intervention will be documented in the lesion count worksheet (see Appendix B). The site will be required to count any lesion that undergoes an intervention as permanently present from the date of the intervention and must account for it in the source and on the appropriate eCRF.

7.1.5. Hidradenitis Suppurativa Pain Numeric Rating Scale

The HS Pain NRS will be completed in a daily diary by participants from screening through EOS. An 11-point scale will be used to assess the worst skin pain and the average skin pain due to HS based on a recall period of the last 24 hours. Ratings for the 2 items range from 0 (no skin pain) to 10 (skin pain as bad as you can imagine).

7.1.6. Analgesic Use

From screening through EOS, participants will complete a daily diary of their analgesic use (yes/no).

7.1.7. Hidradenitis Suppurativa Patient Global Impression of Change

Participants will complete the HS-PGIC questionnaire at the designated study visits. The HS-PGIC consists of 1 self-administered item that assesses change in the severity of skin in the HS area. Participants are asked to indicate their impression of change compared with their last visit. The participant will answer the following: Since your last visit, your HS is: (1) very much improved, (2) much improved, (3) minimally improved, (4) no change, (5) minimally worse, (6) much worse, or (7) very much worse.

7.1.8. Dermatology Life Quality Index

Participants will complete a DLQI questionnaire from screening through EOS. The DLQI will be used to assess the symptoms and the impact of skin problems on quality of life (Hongbo et al 2005). The DLQI can be used to evaluate 6 areas: symptoms and feelings, daily activities, leisure, work and school, personal relationships, and treatment. Participants will be asked to respond to the 10 questions of the DLQI based on a recall period of "the last week." The scoring of each question is as follows:

3 = Very much / Question 7, 'prevented work or studying'

[figure not shown]
2 = A lot

1 = A little

0= Not at all / Not relevant

The DLQI is calculated by summing the score of each question resulting in a maximum of 30 and a minimum of 0. The meaning of DLQI scores can be categorized as follows:

- 0-1 =No effect at all on patient's life
- 2-5 = Small effect on patient's life
- 6-10 = Moderate effect on patient's life
- 11-20 = Very large effect on patient's life
- 21-30 = Extremely large effect on patient's life

7.2. Analysis of Efficacy Endpoints

The efficacy endpoints include:

- Proportion of participants with a HiSCR (at least 50% reduction in AN count with no increase in abscess count and no increase in draining fistula count relative to baseline) at each visit;
- Proportion of participants achieving an AN count of 0 to 2 at each visit;
- Mean change from baseline in the HS Pain NRS scores, worst and average pain, at each visit;
- Mean change from baseline to Week 8 in the modified Sartorius scale score;
- Mean change from baseline in the number of draining fistulas count at each visit;
- Proportion of participants at each category of Hurley Stage at baseline and Week 8;
- Proportion of participants with change from baseline in Hurley Stage at Week 8;
- Proportions of participants in each HS-PGIC category during the treatment period.
- Proportion of participants requiring rescue lesional treatment;

- Number of interventions with rescue lesional treatment;
- Proportion of participants at each scoring category of DLQI at each visit;

Category variables will be summarized using descriptive statistics, including sample size, frequency, and percentages. Continuous variables will be summarized using descriptive statistics, including sample size, mean, median, standard deviation, standard error of the mean, minimum, and maximum.

8. SAFETY AND TOLERABILITY

Sample data displays are provided in Appendix A.

8.1. General Considerations

Summary tables may be replaced with listings when appropriate. For instance, an AE frequency table may be replaced with a listing if it only contains a few unique PTs reported on relatively few participants.

Unless otherwise stated, table summaries will be limited to AEs occurring within 30 days of the last administration of study drug.

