1. PROTOCOL SUMMARY

Protocol Title: A Phase 2, Open-Label, Single-Arm Study of the Safety of INCB054707 in

Participants With Hidradenitis Suppurativa

Protocol Number: INCB 54707-202

Objectives and Endpoints

Table 1 presents the primary and key secondary objectives and endpoints.

Table 1: Primary and Key Secondary Objectives and Endpoints

Objectives	Endpoints				
Primary					
To evaluate the safety and tolerability of INCB054707.	• Frequency, duration, and severity of AEs, clinical laboratory test results, vital signs results, ECGs, and physical examination findings.				
Key Secondary					
To evaluate the systemic exposure to INCB054707.	• Population PK parameters of INCB054707.				
To evaluate the efficacy of INCB054707.	• Proportion of participants with a HiSCR at each visit.				
	 Proportion of participants achieving an AN count of 0 to 2 at each visit. 				
	• Mean change from baseline in the HS Pain NRS scores, worst and average pain, at each visit.				
	 Mean change from baseline to Week 8 in the modified Sartorius scale score. 				
	 Mean change from baseline in the number of draining fistulas count at each visit. 				
	• Proportion of participants at each category of Hurley Stage at baseline and Week 8.				
	 Proportion of participants with change from baseline in Hurley Stage at Week 8. 				
	 Proportions of participants in each HS-PGIC category during the treatment period. 				

Overall Design:

Table 2 presents the key study design elements. Further study details are presented after the table.

 Table 2:
 Key Study Design Elements

Study Phase	Phase 2
Clinical Indication	HS
Population	Men and women aged 18 to 75 years with moderate to severe HS for at least 6 months
Number of Participants	Approximately 10 participants are expected to be enrolled.
Study Design	Multicenter, open-label, and single-arm
Estimated Duration of Study Participation	Up to 28 days for screening, an 8-week open-label, single-arm treatment period, and a 4-week safety follow-up period. The estimated total duration of study participation is approximately 16 weeks for each participant.
Data Safety Monitoring Board	No

Treatment Groups and Duration:

The study design is shown in Figure 1. The schedule of assessments is detailed in Table 3.

Table 3: Schedule of Assessments

		Screening	Treatment				Follow-Up		
Evaluation	Section	Day -28 to -1	Day 1 ^a	Wk 1 ± 1 day	Wk 2 ± 3 days	Wk 4 ^a ± 3 days	Wk 6 ± 3 days	Wk 8a ± 3 days (EOT)	Wk 12 + 7 days (EOS)

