Administrative/screening procedures									
Informed consent	8.1.1	X							
Demography/medical history	8.1.4	X							
Inclusion/exclusion criteria	5	X	X						
Prior/concomitant medications	6.6	X	X	X	X	X	X	X	X
Serology	8.3.5.2	X							
Urinalysis	8.3.5.2	X							
TB screening	8.3.5.2	X							
FSH ^b	8.3.5.2	X							
Pregnancy test ^c	8.3.5.3	X	X	X	X	X	X	X	X
Dispense study drug	6.1		X			X			
Distribute reminder cards	8.1.3	X	X	X	X	X	X	X	
Distribute diary	8.1.3	X	X	X	X	X	X	X	
Collect study drug and assess compliance	6.4			X	X	X	X	X	
Safety procedures/assessments	1	.		•					•
Comprehensive physical examination	8.3.2	X						X	
Targeted physical examination	8.3.2		X	X	X	X	X		X
Vital signs	8.3.3	X	X	X	X	X	X	X	X
Hematology and chemistry assessments	8.3.5.1, 8.6	X	X	X	X	X	X	X	X
Lipid panel	8.3.5.1		X					X	
CRP	8.3.5.1		X					X	
12-lead ECG (screening) ^a	8.3.4	X							
12-lead ECG (predose and postdose) ^d	8.3.4		X						
12-lead ECG (postdose only)d	8.3.4				X		X		
12-lead ECG (predose only) ^d	8.3.4							X	
Assess AEs	8.3.1, 9	X	X	X	X	X	X	X	X
Efficacy assessments		•		•	•		•	•	•
Hurley Stage	8.2.1	X	X					X	X
AN count (HiSCR)	8.2.2	X	X	X	X	X	X	X	X
Modified Sartorius score	8.2.3		X					X	X
Record rescue lesional treatment	8.2.4			X	X	X	X	X	X
HS Pain NRS ^e	8.2.5	X	X	X	X	X	X	X	X
Analgesic use	8.2.6	X	X	X	X	X	X	X	X
HS-PGIC	8.2.7			X	X	X	X	X	X
DLQI	8.2.8	X	X	X	X	X	X	X	X
Optional photography (target area)	8.2.9		X			X		X	

Table 3: Schedule of Assessments (Continued)

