8.1.3. Distribution of Reminder Cards and Diaries

Participants will be provided with a reminder card at the visits indicated at Table 3. The reminder card will indicate the date/time of the next visit and will also remind the participant that they should not take study drug on Day 1, Week 4, and Week 8 visits, as they will take it after blood draws for safety evaluation have been completed. The reminder cards will have an area on which the date and time of the last dose taken (from the previous evening) for Week 4 and Week 8 visits and the time of their last meal before the visit for Day 1, Week 2, Week 4, Week 6, and Week 8 will be recorded.

Diaries will be provided to participants at the visits indicated at Table 3 to record HS pain NRS (see Section 8.2.5) and analgesic use (see Section 8.2.6).

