8.3. Safety Assessments

8.3.1. Adverse Events

Adverse events will be monitored from the time the participant signs the ICF until at least 28 days after the last dose of study treatment. Adverse events that begin or worsen after informed consent should be recorded on the Adverse Event Form in the eCRF regardless of the assumption of a causal relationship with the study drug. Conditions that were already present at the time of informed consent should be recorded on the Medical History Form in the eCRF. Adverse events (including laboratory abnormalities that constitute AEs) should be described using a diagnosis whenever possible rather than by individual underlying signs and symptoms.

Adverse events will be reported by the participant (or, when appropriate, by a caregiver, surrogate, or the participant's legally authorized representative). The investigator and any qualified designees are responsible for detecting, documenting, and recording events that meet the definition of an AE or SAE and remain responsible for following-up on AEs that are serious,

considered related to the study treatment, or that caused the participant to discontinue the study treatment. Care will be taken not to introduce bias when detecting AEs and/or SAEs. Open-ended and nonleading verbal questioning of the participant, such as "How are you feeling?" is the preferred method to inquire about AE occurrences. Adverse events may also be detected when they are volunteered by the participant during the screening process or between visits, or through physical examinations, laboratory tests, or other assessments. The definition, reporting, and recording requirements for AEs are described in Section 9.

All SAEs will be recorded and reported to the sponsor or designee within 24 hours. The investigator will submit any updated SAE data to the sponsor within 24 hours of it being available.

After the initial AE/SAE report, the investigator is required to proactively follow each participant at subsequent visits/contacts. All SAEs will be followed until resolution, stabilization, the event is otherwise explained, or the participant is lost to follow-up (as defined in Section 7.3).

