8.8. Follow-Up

8.8.1. Safety Follow-Up

The safety follow-up period is the interval between the EOT visit and the scheduled safety follow-up visit, which should occur 28 to 35 days after the EOT visit (or after the last dose of study drug if the EOT visit was not performed). Adverse events and SAEs must be reported up until the end of follow-up period, the date of the follow-up visit, or until toxicities resolve, return to baseline, or are deemed irreversible, whichever is longer. Reasonable efforts should be made to have the participant return for the follow-up visit and report any AEs that may occur during this period.

For purposes of analysis, participants who complete through Week 8 will be considered to have completed the study.

9. ADVERSE EVENTS: DEFINITIONS AND PROCEDURES FOR RECORDING, EVALUATING, FOLLOW-UP, AND REPORTING

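### The 30-day cut in SAP 8.1 and 8.3.2 ends inside the protocol's 28-to-35-day follow-up window, so some on-schedule follow-up labs leave the shift tables and AEs starting after day 30 leave the AE tables

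*SAP*

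**What the plan says.** **SAP.** Section 8.1 sets the rule for AE tables: "Unless otherwise stated, table summaries will be limited to AEs occurring within 30 days of the last administration of study drug". Section 8.2 states no other window. Section 8.3.2 limits the worst-postbaseline shift tables to values within 30 days of stopping treatment, or up to the first dose of a next phase if that comes sooner. No day limit is stated for the by-visit laboratory summaries (8.3.1) or for the worst-CTCAE-grade count (8.3.2).

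**Protocol.** Section 8.8.1 describes a safety follow-up visit "which should occur 28 to 35 days after the EOT visit" and adds: "Adverse events and SAEs must be reported up until the end of follow-up period". Table 3 shows this visit at Week 12 with seven days' allowance, late only, and marks both AE assessment and the row "Hematology and chemistry assessments" at it. The nominal plan in Section 4.2 is "a 4-week safety follow-up period". The minimum for AE monitoring in Section 8.3.1 is "until at least 28 days after the last dose of study treatment". Table 13 defines treatment-emergent AEs and worst-postbaseline shifts without an end date.

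Section 8.1.3 fixes when a completer takes the last dose. Participants hold the dose before the Week 8 visit, "as they will take it after blood draws for safety evaluation have been completed". For a completer, last dose and EOT visit therefore normally fall on the same day.

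**The concern.** AEs and laboratory results are the primary endpoint. For a completer, the follow-up sample is the only scheduled blood sample after treatment ends, because the Week 8 sample is drawn before the Week 8 dose. Whether it enters the shift tables (SAP Appendix A 3.3.2, 3.3.3, 3.3.5, 3.3.6) depends on which permitted day the visit took place: day 30 counts and day 31 does not.

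The same day-31 sample still counts in the by-visit laboratory tables, and the same visit counts in efficacy tables that run to Week 12 (Appendix A 2.1.3.1, 2.1.5). Two tables built from one sample can therefore disagree. A worst-grade count, if produced, could also differ from the shift table; Appendix A plans no separate table for it.

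**Working it through.** The documents give no figure for this point, so there is none to reproduce. The check is date arithmetic, with day 30 counted as inside the cut.

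1. **Inputs.** Follow-up visit 28 to 35 days after EOT (protocol 8.8.1): 35 − 28 + 1 = 8 permitted days. Cut at 30 days (SAP 8.1, 8.3.2). Treatment 8 weeks = 56 days. L is the number of days from last dose to the EOT visit.

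2. **Completer, L = 0.** The visit falls 28 to 35 days after the last dose. Days 28, 29 and 30 are inside. Days 31 to 35 are outside: 5 of 8.

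3. **EOT after the last dose.** The visit window runs from EOT but the cut runs from the last dose, so the visit falls on days 28 + L to 35 + L. The number outside is 5 + L, up to 8.

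| L (days) | Visit, days after last dose | Permitted days outside the cut |
|---|---|---|
| 0 | 28–35 | 5 of 8 |
| 1 | 29–36 | 6 of 8 |
| 2 | 30–37 | 7 of 8 |
| 3 | 31–38 | 8 of 8 |
| 14 | 42–49 | 8 of 8 |

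   L = 14 is an illustration. Protocol Table 7 allows interruptions of up to 14 days, so a participant who never restarts could reach EOT that late. Such a participant's EOT sample may itself be off drug, and it stays in the shift table if taken within 30 days.

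4. **Other anchor.** If Week 12 is counted from Day 1 (days 84 to 91) and the Week 8 visit is 3 days early (day 53), the gap is 31 to 38 days and 8 of 8 are outside. On time, the result is 5 of 8. Three days late (day 59), the gap is 25 to 32 days and 2 of 8 are outside.

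5. **AE onset time, completer.** The cut works on when the AE occurs. The longest on-schedule span from first dose is 56 + 35 = 91 days, and at most 35 − 30 = 5 days are lost: 5/91 = 5.5%. With the Week 8 visit 3 days early it is 5/88 = 5.7%; 3 days late, 5/94 = 5.3%.

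6. **Weight of one participant.** With 10 participants, one is 1/10 = 10 percentage points. SAP 8.3.2 uses the baseline category as the shift-table denominator, so one participant is 10 points if all ten share a category and more if they do not.

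7. **How many visits might be affected.** The documents give no distribution of visit days. If an assumed share of 10% of visits fell after day 30, independently, 1 of 10 is expected and the chance of at least one is 1 − 0.9^10 = 65%. At 30% it is 3 expected and 1 − 0.7^10 = 97%. This counts visits, not changed results: a follow-up value alters a worst-value cell only if it is worse than every earlier postbaseline value.

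**The case against.** **The window is an ordinary SAP choice.** The protocol says when AEs are reported and when the visit occurs, not which events are tabulated. The SAP uses 30 days consistently (4.1.4, 8.1, 8.3.2), which covers the protocol's 28-day AE minimum and the nominal four weeks. This stands. A reader might infer from SAP 10.1, which records no change to protocol-defined analyses, that the SAP contradicts the protocol. It does not, because Table 13 is silent on an end date. The problem is that the cut ends before a window the protocol itself permits.

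**Late follow-up is off drug.** Protocol 9.9 ties overdose monitoring to the drug no longer being detectable, at least 3 days. That suggests, without proving, that days 31 to 35 are well off drug. It is a fair reason for some drug-anchored cut, but it applies equally to days 28 to 30, which are kept. It does not explain a line between day 30 and day 31.

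**Nothing is hidden.** All AEs are listed whatever their timing (SAP 8.2.1), hematology and chemistry values are listed, and small AE tables may be replaced by listings (8.1). In a single-arm study of about 10 without a hypothesis test, listings carry much of the safety reading. This stands and limits the point to tables.

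**Two stronger readings fail.** One is that a visit on days 31 to 35 drops out of the AE tables altogether. It does not: an AE recorded at that visit with onset by day 30 stays. The other is that 5 of 8 means a 62.5% chance of exclusion. Day 28 is the nominal target, and nothing supports an even spread over the window.

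**Conclusion.** The point holds as a cheap improvement that should be made. It is not a flaw that endangers the trial. For completers dosing at EOT, laboratory values from an on-schedule visit on days 31 to 35 leave the shift tables while the by-visit summaries keep them. AE tables lose only events occurring after day 30, at most 5 of about 91 days. If EOT is 3 or more days after the last dose, every permitted follow-up day is outside the shift-table cut. On-treatment samples, and visits on days 28 to 30 after the last dose, are unaffected.

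This assumes that the visit window runs from EOT as in protocol 8.8.1, and that stopping treatment in SAP 8.3.2 means the last dose. If it meant a later discontinuation date, the extra loss from L would shrink for the shift tables but not for the AE tables, whose cut runs from the last administration.

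A minor side note, not needed for the finding: SAP 8.4 defines an alert vital sign as out of range and changed by more than 25%. Read as change from baseline, no fever can meet this for temperature. From an assumed baseline of 36.0 C the alert needs more than 1.25 × 36.0 = 45.0 C. Values above 38 C are still listed as clinically notable, so only the alert listing is affected.

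**What to change.** In SAP 8.1 and 8.3.2, run the AE tables, the shift tables and any worst-CTCAE-grade summary through the safety follow-up visit or 30 days after the last dose, whichever is later. Keep the existing next-phase clause. Add a flag for time since last dose, so that the 30-day version can be recovered and off-drug findings can be seen as such.

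All 8 permitted visit days are then kept at any L. Simply moving the cut to 35 days would not achieve this: it keeps 8 of 8 at L = 0, but 7 at L = 1, 5 at L = 3 and none at L = 14.

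The cost is SAP wording and minor programming, with no new data. The downside is that some off-drug events or values enter the tables and the counting window varies between participants. It is 30 to 35 days after the last dose for completers, and up to 35 + L days when EOT is L days after the last dose (49 at L = 14). The flag makes both visible.
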